We will recruit 280 participants; 70 in each of the four arms. Wiberg-Itzel et al [2] observed mean umbilical artery pH 7.23 (SD 0.07) in the non-intervention group. With our sample size, we will have 80% power (significance level 0.05) to detect mean pH changes of 0.04 and above in each arm. We are interested in detecting an effect size of 0.2 and above, which we deem to be a moderate effect size. The total sample size needed to detect a between-factor mean effect size of 0.2, by repeated measures analysis of variance (ANOVA) with a type 1 error margin of 5%, across 4 groups with 5 repeated measurements; was 224 at a power of 91%. Assuming a 20% loss to follow up in our study; we will need 280 participants (70 in each of the 4 groups). The sample size was calculated using G* Power software version 3.1 using the test family for the F test, and the statistical test for ANOVA repeated measures, between factor analysis & within-between interaction [10]. Therefore, our sample size will also be sufficient to detect a within and between-subject interaction (intervention and time interaction) with a power of 99%. To obtain these estimates, we will construct an interaction term between the intervention and the time variable. We are confident that we shall be able to accrue this number of participants in a period of six calendar months, on the basis of our experience working in the same hospital [7]. In order to detect a change in maternal pH, a minimum of two measurements are needed from a participant. However, with improvement of obstetric care, many women deliver within 30 minutes of taking the baseline measurements and hence no second measurement is obtained. To account for this form of right censoring, we have inflated our sample size by 192 participants to ensure that we have at least 280 women with at least two pH measurements. We will recruit 472 participants; 118 in each of the four arms.

Outcome variables

The primary outcome measure will be the mean change in maternal pH from baseline in each group. The secondary outcomes will include, mean pH and lactate in maternal and umbilical blood, early neonatal death, safety (side effects) of sodium bicarbonate, primary PPH, sepsis and death. Furthermore, the plasma concentrations of HCO₃ levels will be measured as well to accurately estimate the required dose.

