Secondary outcomes will include neonatal death, postpartum haemorrhage and sepsis, in addition to the pharmacokinetics of sodium bicarbonate infusion in pregnant women. Details of measurements are in table 1.

The independent variables will include the sociodemographic, clinical, and obstetric characteristics of the study participants at different time points as indicated in table 1.

Table 1: Measurements to be taken from the participant samples

Activity/ procedure	Time in minutes							Comment
	Baseline (0)	30	60	90	120	150	At birth	
Metabolites (lactate & glucose)	X	X	X	X	X	X		Bedside using the RAPID Point 500e or YSTE-BG100 Blood gas analyzer
Blood gases (pH, pCO ₂ , pO ₂)	X	X	X	X	X	X	X	
Serum Electrolytes (Na ⁺ , K ⁺ , Ca ²⁺ , Cl ⁻)	X	X	X	X	X	X	X	
Umbilical cord blood for lactate							X	Bedside using the RAPID Point 500e or YSTE-BG100 Blood gas analyzer
Myometrial Lactate only collected at Caesarean section							X	Bedside using the RAPID Point 500e or YSTE-BG100 Blood gas analyzer
Creatinine	X							Total of 5 mL of venous blood will be taken to a central laboratory; these are part of the standard care for each patient.
Liver function tests (ALT&AST)	X							
Full blood count	X							
Amniotic fluid lactate*	X							Lactate Pro device
Bicarbonate concentrations in plasma	X	X	X	X	X	X	X	Bedside using the RAPID Point 500e or YSTE-BG100 Blood gas analyzer

[figure not shown]

Figure 2: Flow of participants in the trial from screening to analysis

Recruitment and data collection from participants

Participants: Obstructed labour will be diagnosed by either an obstetrician or medical officer using a definition of the American Association of Obstetricians and Gynaecologists (ACOG). In the first stage of labour, the participant should have cervical dilatation >6 cm with ruptured membranes, adequate contractions lasting >4 hours with no change in cervical dilatation or delay in the second active stage of labour (nullipara >2 hours, multipara >1 hour) with adequate uterine contractions. In addition, any two of: the obvious signs of severe obstruction such as caput formation, severe moulding, Bandl's ring, subconjunctival haemorrhages or an oedematous vulva.

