Data analysis plan

Data will be analyzed using Stata version 17.0 (StataCorp; College Station, TX, USA). We will describe categorical variables as proportions and compare them with chi-squared tests or Fischer's exact tests as appropriate. We will describe continuous variables as means (SD) OR medians (IQR) and compare them with t tests or Mann-Whitney U tests as appropriate. Our analysis will be by intention to treat. To determine the safety of sodium bicarbonate infusion, we will compare the incidence of side effects in each arm and report risk differences.

For the primary outcome of acidosis (pH and lactate) between-subjects repeated measures ANOVA will be conducted. We will also conduct within-subject interaction repeated measures ANOVA to assess for differences in the rate of change of pH between the groups.

We will use histograms, P-P plots, k-density, and Q-Q to assess the distribution of normality of continuous outcomes. In case the distribution of normality is not met; we shall transform our data and this decision will be guided by Stata's *gladder* command that shows various transformation options.

All analyses will be followed by a Bonferroni posthoc test for multiple comparisons, a Friedman test to compare rates of change between the various groups, and a Mauchly's test of Sphericity to check for equal variance among the combinations of the various groups. We will use Margins and Margins plots to obtain marginal means and graphical descriptions of the interaction between various groups and time.

Data Monitoring

Independent Data Monitoring Committee (IDMC)

An independent data monitoring committee (IDMC) will be appointed consisting of 3 members: a statistician, an obstetrician/gynaecologist, and a paediatrician. They will operate according to the IDMC charter, which will be developed with the members. IDMC will be encouraged to follow the recommendations of the international DAMOCLES group for IDMC activities.[12] The IDMC will monitor the trial once with a focus on issues relating to the quality of trial conduct, such as overall and site-specific rates of recruitment, adherence to trial interventions, visit schedules, losses to follow-up, and administrative and safety data. It will review administrative and safety data approximately every three months. The treatment groups will be masked in the IDMC reports.

Interim analyses and stopping guidelines

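### Mauchly's test is misdescribed and no correction is tied to it, so the additional arm-by-time test of pH, run as written, would reject too often if sphericity fails

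*Combined protocol and SAP*

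**What the plan says.** Under Outcome variables the primary endpoint is a change: "The primary outcome measure will be the mean change in maternal pH from baseline in each group".

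The Data analysis plan then gives two repeated measures analyses. The first is "For the primary outcome of acidosis (pH and lactate) between-subjects repeated measures ANOVA will be conducted". The second is introduced as an addition: "We will also conduct within-subject interaction repeated measures ANOVA to assess for differences in the rate of change of pH between the groups".

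Later in that section, in a list of procedures to follow all analyses, comes Mauchly's "test of Sphericity to check for equal variance among the combinations of the various groups". Nothing is said about what the analyst does with the result: no Greenhouse-Geisser or Huynh-Feldt adjustment, no multivariate test and no mixed model. For non-normality, by contrast, the same section does give a response (transformation).

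Table 1 schedules blood gases at 0, 30, 60, 90, 120 and 150 minutes and at birth. The sample size section assumes five repeated measurements.

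**The concern.** Sphericity means that the differences between any two time points have the same variance across women. It is a property of the within-woman covariance, and equal variance among arms is a separate matter. The sentence therefore gives the test the wrong purpose and leaves it without a consequence.

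This matters for the arm-by-time F test. When sphericity fails, the usual degrees of freedom are too large and the p-value too small. Serial pH after a single bolus is a setting where failure is likely, because readings 30 minutes apart should resemble each other more than readings two hours apart.

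The arm-by-time test is the added analysis, but of the two it lies closer to change from baseline. The plan does not say which is confirmatory. The interim stopping rule uses p ≤ 0.003 on the primary outcome without saying which test supplies that p-value.

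**Working it through.** **Inputs from the documents.** Alpha 0.05, four groups, five measurements and N = 224 ("with a type 1 error margin of 5%, across 4 groups with 5 repeated measurements; was 224 at a power of 91"%), with effect size f = 0.2; six scheduled times from 0 to 150 minutes (Table 1); an interim look at 140 women with threshold 0.003.

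**Inputs the documents do not give.** The within-woman correlation of pH and the nonsphericity factor epsilon. Both are assumed below and varied.

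**1. The plan's own figures.** With m = 5 and an assumed correlation of 0.5:
- Between-arm test: λ = f²·N·m / (1 + (m−1)ρ) = 0.04 × 224 × 5 / 3 = 14.93 on 3 and 220 df. Power is 91.06% (stated: 91%).
- Loss to follow-up: 224 / 0.8 = 280, as stated.
- Interaction: λ = f²·N·m·ε / (1 − ρ) = 0.04 × 224 × 5 / 0.5 = 89.6 on 12 and 880 df at ε = 1. Power is above 99.9% (stated: 99%).

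The stated figures are consistent with ρ = 0.5 and ε = 1, that is, with sphericity taken for granted.

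**2. Error rate of the uncorrected interaction test.** Let λ₁, …, λₘ₋₁ be the eigenvalues of the within-woman covariance after each woman's mean is removed. With no drug effect,

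F = [Σ λⱼ χ²(3) / (3(m−1))] / [Σ λⱼ χ²(220) / (220(m−1))],

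and ε = (Σλⱼ)² / ((m−1) Σλⱼ²). The plan as written refers F to 3(m−1) and 220(m−1) df. Greenhouse-Geisser multiplies both by ε. For example, with m = 5 and AR(1) 0.7, ε = 0.689. The df fall from 12 and 880 to about 8.3 and 606, and the 5% critical value rises from 1.76 to 1.94.

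Rejection rates at nominal 5%, N = 224, complete data, at least 400,000 draws per cell:

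| Readings | Constant correlation | AR(1) 0.5 | AR(1) 0.7 | AR(1) 0.9 |
|---|---|---|---|---|
| 2 | 5.0% | 5.0% | 5.0% | 5.0% |
| 3 | 5.0% | 5.5% | 5.9% | 6.3% |
| 4 | 5.0% | 6.1% | 6.9% | 7.8% |
| 5 | 5.0% | 6.6% | 7.9% | 9.1% |
| 6 | 5.0% | 7.0% | 8.6% | 10.4% |

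With N = 140 or 280 and five readings the rates are nearly the same.

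**3. Other covariance shapes.** A random intercept plus AR(1) plus measurement error gives 5.9–6.3% (five readings) and 6.2–7.0% (six). Random slopes of increasing strength give 5.1–10.5% and 5.5–13.0%.

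**4. Full-data simulation** (6,000 trials per setting, AR(1) 0.5/0.7/0.9, five and six readings). With ε estimated from the data, the Greenhouse-Geisser test rejects in 4.8–5.7%. The between-subjects test rejects in 4.5–5.2%. Mauchly's test rejects in every trial.

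**5. Interim threshold, if the interaction test were the one used.** At nominal 0.3% with 140 women, the uncorrected rate is 0.3% under constant correlation. Under AR(1) 0.5 to 0.9 it is about 0.8–1.8% with five readings and 0.9–2.5% with six. With the correction (true ε) it is 0.4–0.5%.

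**The case against.** - **Size.** A reader might infer that the test will run at about 8 to 10%. The documents do not support that. It needs strong AR(1) correlation and complete series of five or six readings. Stable differences between women plus measurement error bring the rate down to about 6 or 7%. The average wait for caesarean section is given as about 110 minutes, which allows only four scheduled readings (0, 30, 60, 90), and the sample size section expects many women to deliver within 30 minutes. Inflation is smaller with fewer readings and absent with two. This objection stands.

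- **Role.** A reader might also infer that the primary analysis is compromised. The plan names the between-subjects test for the primary outcome and bases the 224 on it, and sphericity does not affect that test. This stands too. What remains is that the plan declares neither test confirmatory, for the final or the interim analysis.

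- **Intent.** The plan does not refuse a correction, and listing Mauchly's test suggests that the authors meant to act on it. That is fair, but a pre-specified plan has to fix which p-value counts.

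- **Wording.** The phrase may be a garbled textbook definition in which related groups are time points. Whatever the sentence calls it, software would test the within-woman covariance, so it cannot be assumed that an analyst would miss the violation. Against this, the same paragraph uses groups to mean arms. The wording is in any case the smaller fault; the missing rule is the larger.

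**Conclusion.** The point holds in a limited form. The purpose given for Mauchly's test is wrong and no action is attached to it. If the additional arm-by-time ANOVA is run as written, it rejects too often whenever sphericity fails, which is likely here. The excess runs from nothing under constant correlation to about double the nominal 5% under strong serial correlation with six readings (10.4%), and strong random slopes could take it to 13%. All of these figures rest on assumed covariances and complete series. Classical repeated measures ANOVA handles incomplete series poorly, so the rate in this trial could differ. The interim figures apply only if the interaction test supplies the interim p-value, which the plan leaves open. Worth fixing, not must-fix.

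**What to change.** Replace the Mauchly sentence with:

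*Tests involving time will come from a mixed model with unstructured within-woman covariance, which also uses incomplete series from women who deliver early, or, if repeated measures ANOVA is kept, will use Greenhouse-Geisser adjusted degrees of freedom whatever the result of any sphericity test.*

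Add a second sentence that names the confirmatory test and says that the same test supplies the interim p-value. If unequal variance between arms is a separate worry, deal with it separately, with arm-specific residual variances or robust standard errors.

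The cost is two sentences and a slightly less favourable interaction p-value. On the plan's own power inputs (ρ = 0.5, N = 224, m = 5) the loss is small: even at the lowest possible ε, 1/(m−1) = 0.25, interaction power is 98.5%. Of the two options the mixed model suits this trial better because short series are expected. Few women may reach 150 minutes, so a simpler covariance should be named in advance in case the unstructured fit does not converge.

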Obstructed labor is a major problem that accounts for 22% of maternal deaths and 70% of perinatal deaths due to intrapartum asphyxia in low resource settings [4]. In Uganda, half of the 26,000 perinatal deaths audited and reported in 2021/2022 were due to intrapartum birth asphyxia [5]. The maternal and fetal harm of OL comes from intrapartum asphyxia, characterized by accumulation of hydrogen ions that cross the placental barrier to cause fetal acidosis. Acidosis causes failure of basic cellular functions resulting into cell death, especially if it remains uncorrected for an extended period. In a recent RCT, we found that 61% of 477 women with OL were acidotic (lactate >4.8 mmol/L), with a median capillary blood lactate level of 6.9 (3.4–13) mmol/L. In Mbale hospital, perinatal mortality rate is twice the national average of 48 per 1,000 total births [6]. In the Sodium Bicarbonate in Obstructed Labour (SoBicOL) trial, 34% of the newborns had an Apgar score of less than seven, and 12% resulted in early neonatal deaths despite being resuscitated [7]. At two years of age, two thirds of the children born in this cohort had a neurodevelopmental delay [8]. These adverse outcomes may be averted by correcting the metabolic acidosis in obstructed.

Currently, preoperative intravenous fluid infusion (1.5L of normal saline) is a component of the standard preoperative care for all women with OL [9]. Although this practice is adequate to correct electrolyte imbalances and dehydration in most women, it may not be sufficient to reverse the metabolic acidosis. In the SoBicOL trial [7], a single dose of 4.2g was insufficient to achieve significant changes in maternal or neonatal lactate levels in comparison to a placebo. We postulate that our choice of a single dose regimen was too conservative, and only one measurement for the primary outcome at one hour was not ideal. The effect of sodium bicarbonate on maternal blood lactate was only noticeable more than one hour after the intervention. Currently, it is not known if a higher dose of bicarbonate would reverse the acidosis and achieve clinical benefits for the mother and baby.

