Interim analyses: The interim analysis of efficacy data will be performed by the IDMC statistician. One analysis will be conducted according to the group sequential design when 50% of the inclusions are recorded. According to the O'Brien-Fleming alpha spending function, using a group sequential design and assuming a power of 80% and a significance level of 5%, the first interim analysis includes 140 subjects and has an information rate of 50%, efficacy bounds of -2.96 and 2.96, and p-value 0.003 (figure 3). These calculations were made using the RPACT RShiny app (<https://rpact.shinyapps.io/public/>). Interim trial data will be kept confidential and restricted to the IDMC, except if early stopping of the trial is recommended.

[figure not shown]

Figure 3: Figure showing efficacy bounds (critical value) at the interim analyses (50% accrual rate) and how these will change as the study progresses

Stopping guidelines

1. We propose the following stopping rule: “a statistically significant difference ($p \leq 0.003$) at the interim analysis according to the O'Brien-Fleming spending function for group sequential design) in the primary outcome between the treatment arms.
2. SAEs will be continuously monitored during data entry and reported to the IDMC. Any imbalance between expected occurrence and actual occurrence will be assessed by the IDMC statistician when 50% inclusions are recorded, and discussed with the IDMC.
3. The IDMC will provide a recommendation to stop or alter the design or conduct of the trial in case of high efficacy and/or poor adherence or unacceptable side effects that can be ascribed to the intervention according to pre-determined stopping rules and criteria. While the reviews of safety will consider both expected or unexpected adverse events, and the relative rates of death.
4. If the IDMC recommends stopping the trial early, a meeting of the principal investigator, the trial sponsor, the trial steering committee and the IDMC will be held to decide on the trial discontinuation. In case of disagreement, the advice of independent external experts will be sought. A report will be submitted to the Local IRB (BUIRB) as soon as possible and not later than 14 days after the decision.

Ethics and consent process

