We plan to conduct one interim analysis, when half (25%) of the participants have been recruited. This will be undertaken by the independent data monitoring committee (IDMC) composed of an obstetrician, a paediatrician and a statistician with research experience. These will be appointed by the sponsor of the study, Busitema University. The stopping rules agreed upon in the terms of reference for the IDMC will be based on: safety concerns, outstanding benefit, and futility. The IDMC will have the mandate to halt the study if the occurrence of adverse events (Safety) in any of the intervention arms is greater or equal to 10% in comparison to the placebo arm. All the serious adverse events (SAE's) will be reported and closely followed, until resolution following the existing statutory guidelines. However, this is unlikely to happen because the active drug (sodium bicarbonate) has a very good safety profile in both clinical use and research even among pregnant women in children. Furthermore, we will ensure that our study protocol is approved by both the Busitema University Faculty of Health Sciences Research and Ethics committee (BUFHS), and the Uganda National Council for Science and Technology (UNCST).

Quality control: All our research assistants will be qualified midwives/nurses, with training in good clinical practice (GCP). They will also receive training in the study protocol procedures during the trial dry run phase and at regular intervals throughout the implementation of the trial. The electronic questionnaire will be coded with checks and skips to ensure internal consistency. All the required blood tests will be done at the bedside using the RAPIDPoint® 500e Blood Gas System (Siemens Healthcare GmbH)[16]. Our choice of this system was informed by its ability to measure a range of parameters, using only 100 microliters of blood. Additionally, women with obstructed labour requiring urgent intervention, hence the need for a

BUFHS-2024-164_Protocol_SoBicOL-II Study_V1.3_10 September 2025_Page 14 of 25

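### IDMC reports mask the treatment groups, but the safety stopping rule compares each dose arm with placebo, and nothing says how the IDMC learns which arm is which

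*Combined protocol and SAP*

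**What the plan says.** Three places bear on this point.

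- **Data Monitoring, Independent Data Monitoring Committee (IDMC).** After describing a safety review about every three months, the section says: "The treatment groups will be masked in the IDMC reports". The charter is still to be developed with the members.
- **Interim analyses and stopping guidelines.** The IDMC statistician performs the interim efficacy analysis at 140 subjects, and interim data are restricted to the IDMC. On serious adverse events: "Any imbalance between expected occurrence and actual occurrence will be assessed by the IDMC statistician when 50% inclusions are recorded". The IDMC may recommend stopping the trial, or altering its design or conduct, for "unacceptable side effects that can be ascribed to the intervention according to pre-determined stopping rules and criteria". A recommendation to stop goes to a joint meeting with the investigator, sponsor and steering committee.
- **Independent Data Monitoring Committee (after Management).** On the committee's power, this section says: "The IDMC will have the mandate to halt the study". The safety trigger for using that power is worded as a comparison with placebo: "adverse events (Safety) in any of the intervention arms is greater or equal to 10% in comparison to the placebo arm".

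Allocation is 1:1:1:1 to placebo and three doses (8.4, 12.6 and 16.8 g). No section describes an arm key, a closed unmasked report or an unmasking trigger for the IDMC.

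**The concern.** The stopping rule takes placebo as its reference, and the report is written so that placebo cannot be identified. The second criterion, side effects ascribed to the intervention, also needs to know who received it. A team that follows the text literally would hand the IDMC data on which the rule cannot be confirmed.

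In a dose-ranging trial the order of the arms matters as much as the placebo label. A rate that climbs from placebo to the top dose is a different finding from the same four rates in another order, and masked reports do not separate the two. All three doses exceed the 4.2 g of the earlier trial, the highest by 16.8/4.2 = 4 times, and no staggered opening of the arms is described. That is context for why the between-arm comparison is wanted; it does not measure the masking problem.

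**Working it through.** **The plan's own figure.** The safety rule comes with no operating figures. The only computable interim figure is the efficacy bound. O'Brien-Fleming-type spending at 50% information, 0.025 per side, spends 2[1 − Φ(z₀.₉₈₇₅/√0.5)] = 0.001525 per side. This gives z = 2.963 and two-sided p = 0.00305, matching the stated 2.96 and 0.003. The bound is not in dispute; the section supplies the interim size, 140/4 = 35 per arm.

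**What coded arms allow.** Suppose the report shows arms A to D and 10% means percentage points. Try each label in turn as placebo.

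- If the highest-rate arm is placebo, no active arm exceeds it and the rule is not met, whatever the data.
- If the lowest-rate arm is placebo, the rule is met exactly when max − min ≥ 10 points.

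So if max − min < 10 points, the rule is ruled out under every labelling. Otherwise the answer depends on which label is placebo. No data set confirms the rule under all labellings.

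Example at 35 per arm: event counts 7, 7, 7, 3. If the arm with 3 is placebo, the excess is (7 − 3)/35 = 11.4 points and the rule is met. Under the other three labellings it is not.

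**How often this happens.** Assumptions: independent binomial arms, and event rates chosen for illustration because the documents give none. At 35 per arm, 10 points is 3.5 events, so a gap of at least 4. With f and F the binomial probability and distribution functions, and arm 0 as placebo:

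- P(rule met, arms known) = 1 − Σₓ f₀(x)·F₁(x+3)·F₂(x+3)·F₃(x+3)
- P(undecidable, arms coded) = P(max − min ≥ 4)

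| Assumed rates (placebo to top dose) | Per arm | Rule met, arms known | Undecidable, arms coded |
|---|---|---|---|
| 10% in all arms | 35 | 19% | 49% |
| 20% in all arms | 35 | 31% | 72% |
| 30% in all arms | 35 | 36% | 80% |
| 10/15/20/30% | 35 | about 90% | 95% |
| 10% in all arms | 59 | 12% | 32% |
| 30% in all arms | 59 | 29% | 68% |
| 10/15/20/30% | 59 | 95% | 97% |

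The 59-per-arm rows take half of the 472 target (236/4 = 59; threshold 6 events). They are shown because the documents also give that larger target.

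**Dose order.** Four labels can be assigned in 4! = 24 ways, and one is true. Sorting coded arms by observed rate does not recover it: under 10/15/20/30% at 35 per arm, the observed counts rise strictly in the true order in only about 26% of simulated trials.

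**If masked means pooled.** There are no between-arm differences to read, so the rule can be neither ruled out nor confirmed.

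**The case against.** The best defence is that the sentence masks the reports and does not say that the committee is denied the key. The statistician is an IDMC member, runs the interim efficacy analysis, and could hold the code. The sentence follows the three-monthly review and may describe only those routine reports. The charter is unwritten and could settle access. Infusion volumes differ by arm (50 to 200 mL), so administration data might reveal identity anyway.

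Part of this stands. A reader might infer that the IDMC cannot use its rule at all. The documents do not support that: the statistician's access is unstated rather than refused, and coded arms still let the committee rule the threshold out. The expected-versus-actual check of serious adverse events and an overall efficacy test need no labels.

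A reader might also infer that the IDMC is the only control on dose-related harm. The documents contradict this: midwives monitor each woman actively for 24 hours, side effects are checked hourly at first, blood gases and electrolytes are scheduled every 30 minutes, and serious adverse events are monitored continuously.

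Finally, a reader might take the undecidable percentages as chances of a false halt. They are not. No rule to stop when any two coded arms differ appears in the plan. The 19% to 36% chance triggers under equal rates at 35 per arm come from the threshold itself and would remain after arm identity is supplied.

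The rest does not remove the conflict. The three-monthly reports are where safety data are reviewed. A charter that unmasked those reports would contradict the protocol. Informal identification from volumes is no substitute for a stated access rule.

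**Conclusion.** The conflict is in the current text, and nothing in the documents resolves it. As written, the committee given a placebo-referenced safety rule receives reports that hide placebo, with no stated route to arm identity. With coded arms it can exclude the rule but not confirm it, and it cannot see a dose trend. With pooled reports it can do neither.

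Masking bites hardest in the situation that the rule exists to catch: under the assumed dose-ordered harm, the rule is nearly always met with arms known and nearly always undecidable with arms coded. These sizes rest on assumed event rates, on 10% meaning percentage points, and on masked meaning four coded arms. The logical result, that coded arms never confirm the rule, does not depend on the event rates.

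The gap concerns between-arm safety stopping, not safety monitoring as a whole.

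**What to change.** Reconcile the two IDMC sections and the stopping guidelines.

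1. Replace the masking sentence with one stating that the IDMC statistician prepares a closed report for the IDMC that identifies placebo and the three doses in order, while investigators, site staff and sponsor stay masked. At minimum, state that the IDMC statistician holds the key and reports each arm-versus-placebo comparison to the committee. Say in which reports this applies and when.
2. Reconcile the mandate to halt the study with the power to recommend stopping or altering it, and say whether an action can apply to one arm.
3. State whether 10% is absolute or relative. This review proposes no threshold.

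The cost is a few sentences in the protocol and matching text in a charter that has yet to be written. The randomisation list already exists with the independent biostatistician and the off-site pharmacist. The downside is that IDMC members see arm identity. The exposure is limited to a closed report, and interim data are already restricted to the committee.
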